OBJECTIVES	
Primary Objectives:
 
 1) To estimate objective response (OR) rate (ORR) to nivolumab and cabiralizumab in relapsed/refractory peripheral T cell lymphoma (PTCL) by LYRIC criteria at 4 months 2) To estimate complete response (CR) rate (CRR) to nivolumab and cabiralizumab in relapsed/refractory peripheral T cell lymphoma (PTCL) by LYRIC criteria at 4 months 
Secondary Objectives:
 
 1) To estimate ORR and CRR of this combination by Lugano criteria at 4 months. 2) To estimate the best OR (including PR and CR) at any time on trial by LYRIC and Lugano criteria 3) To estimate progression free survival (PFS), disease control rate (DCR), duration of response (DOR), and time to next treatment (TNT). 4) To evaluate the safety and tolerability of the combination of cabiralizumab and nivolumab. 
Exploratory Objectives:
 
 1) To determine lymphoma associated macrophage (LAM), regulatory T cell (Treg), and cytotoxic T lymphocyte (CTL) densities (before and during treatment) as pharmacodynamic and prognostic biomarkers. 2) To determine lymphoma cell and tumor microenvironment expression of PD-L1 and CSF-1R as pharmacodynamic and prognostic biomarkers. 3) To examine the abundance of “exhausted” T cells in the peripheral blood as a pharmacodynamic and prognostic biomarker. 4) To evaluate the feasibility and utility of minimal residual disease monitoring throughout treatment as a pharmacodynamic and prognostic biomarker. 5) To evaluate the role of myeloid derived suppressor cells as a pharmacodynamic and prognostic biomarker. 6) To biobank diagnostic biopsy specimens and PBMC for future correlative studies.
STUDY DESIGN	Open label, single arm, non-randomized trial
KEY ELIGIBILITY CRITERIA	
Inclusion criteria:
 
 1) Able to voluntarily provide written IRB-approved informed consent. 2) At least 18 years of age or older at the time of enrollment. 3) ECOG Performance Status of 0-2 4) Histologic confirmation of peripheral T-cell lymphoma (PTCL) with measurable disease on imaging. Adult T-cell leukemia/lymphoma (ATLL) are excluded.

- 5) Documented disease progression after receiving at least two prior therapeutic regimens including brentuximab vedotin in patients with CD30 positive disease (defined as >10% CD30 positive cells).
- 6) Prior cancer treatment must be completed at least 28 days prior to treatment and the subject must have recovered from all treatment related toxicities (less than grade 3) or returned to baseline prior to treatment. Steroids at <10 mg prednisone equivalent daily allowed.
- 7) Adequate hematological function:
 - a. ANC \geq 1,000 cells/uL
 - b. Platelets \geq 75,000 cells/uL
- 8) Adequate renal function:
 - a. Serum creatinine \leq 1.5 x ULN, or calculated creatinine clearance >30 mL/min.
- 9) Adequate hepatic function:
 - a. Bilirubin \leq 1.5 times the specific institutional upper limit of normal (ULN) (except patients with Gilbert's syndrome, who must have total bilirubin <3 mg/dL)
 - b. AST and ALT each \leq 1.5 x ULN (or \leq 2.0 x ULN in the presence of known or suspected hepatic involvement)
- 10) Women of childbearing potential (WOCBP) must have a negative serum or urine pregnancy test (minimum sensitivity of 25 IU/L or equivalent units of human chorionic gonadotropin) performed at screening and within 24 hours prior to the start of study treatment.
- 11) Females of childbearing potential must be willing to abstain from heterosexual activity or use an effective method of contraception from the time of informed consent until 5 months after the last dose of investigational product
- 12) Men who are sexually active with WOCBP must use any contraceptive method with a failure rate of less than 1% per year. Men receiving study drugs and who are sexually active with WOCBP will be instructed to adhere to contraception for a period of 7 months after the last dose of investigational product.
- 13) Able to understand and comply with study procedures.

Exclusion Criteria:

- 1) PTCL histology consistent with ATLL
- 2) A history of, or a concurrent, clinically significant illness, medical condition or laboratory abnormality that, in the investigator's opinion, could affect the conduct of the study.
- 3) Active infection requiring systemic therapy.
- 4) Recent (<100 days) autologous stem cell transplant, or previous allogeneic stem cell transplant.
- 5) Known positive test for hepatitis B surface antigen, hepatitis C, or HIV
- 6) Pregnant or breastfeeding female.
- 7) Known additional malignancy that is active/progressive requiring treatment. Exceptions include:
 - a. basal cell skin cancer

[figure not shown]
	
 b. squamous cell skin cancer c. in situ cervical cancer d. in situ bladder cancer 
8) Prior treatment with cabiralizumab 9) Prior treatment with nivolumab or other medications within the checkpoint blockade family.
 
Please see body of protocol for full exclusion criteria.

STATISTICAL CONSIDERATIONS	
We propose a two-stage design with co-primary endpoints of complete response (CR) and overall response (OR), testing a “both-and” null hypothesis against an “either-or” alternative hypothesis. Specifically, we posit that a CRR of 30% or ORR of 60% is achievable. Initially, 17 eligible patients will be followed for response. At this point, if fewer than 3 patients demonstrate CR (<18%) and fewer than 7 patients demonstrate OR (<41%), the trial will be stopped for futility. Otherwise, we will enroll an additional 16 patients, and the trial will successfully conclude if at least 7 patients (out of 33 total) demonstrate CR (21%) or at least 17 patients demonstrate OR (52%). When the true CRR and ORR are simultaneously no greater than 10% and 30%, respectively, this design will successfully conclude with probability at most 0.05 (one-sided type I error) and stop at the interim analysis with probability at least 0.75. When the true CRR is at least 30% or the true ORR is at least 60%, this design will successfully conclude with probability at least 0.62 (power) and stop for futility at the interim analysis with probability at most 0.34.
 
Multiple Grade 4+ adverse event (AE) stopping rules will be applied during enrollment of the first 17 patients. First, enrollment will stop for any grade 4 AE observed in ≥ 7 (7/17=41%) patients. Second, enrollment will stop for grade 4 AE requiring discontinuation of treatment, as specified in the protocol, observed in ≥ 3 (3/17=12%) of patients. Third, enrollment will stop if any Grade 5 AE is observed within the first 17 subjects.
 
Peripheral T-cell lymphoma response and progression will be assessed using the provisional Lugano lymphoma response to immunomodulatory therapy criteria (LYRIC). Additional secondary endpoints include response by Lugano criteria, PFS, DCR, DOR, and TNT. Safety assessments will consist of the surveillance and recording of AEs and documentation of physical examination findings and laboratory data. Type, incidence, severity, seriousness, and relatedness of adverse events will be recorded.

TOTAL NUMBER OF SUBJECTS	33

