12.3 Sample Size, Accrual, and Interim Futility Analysis

We propose a two-stage design with co-primary endpoints of complete response (CR) and overall response (OR), testing a “both-and” null hypothesis against an “either-or” alternative hypothesis. Specifically, we posit that a CRR of 30% or ORR of 60% is achievable (note that CRR refers to the *marginal* CRR, that is, the complete response rate without respect to overall response status, and not the *conditional* CRR, which would be the complete response rate among any responders). Initially, 17 eligible patients will be followed for response. At this point, if fewer than 3 patients demonstrate CR (<18%) and fewer than 7 patients demonstrate OR (<41%), the trial will be stopped for futility.

Otherwise, we will enroll an additional 16 patients, and the trial will successfully conclude if at least 7 patients (out of 33 total) demonstrate CR (21%) or at least 17 patients demonstrate OR (52%).

We will also formally incorporate three Grade 4+ adverse event (AE) thresholds that will activate at the interim analysis. First, if the number of patients with any Grade 4 AE is greater than or equal to 7 (7/17=41%) by the interim analysis, enrollment will stop. Second, if the number of patients with Grade 4 AEs that *require discontinuation of study treatment, as specified in section 6.3*, is greater than or equal to 3 (3/17=12%) by the interim analysis, enrollment will stop. Third, enrollment will stop at the interim analysis for any Grade 5 AE attributable to drug.

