To demonstrate the operating characteristics of this design, we simulated repeated trials under a grid of different true values of CRR, ORR, and Grade 4+ AE rate. When the true CRR and ORR are simultaneously no greater than 10% and 30%, respectively, and the true Grade 4+ AE rate is 32%, this design will successfully conclude with probability less than 0.05 (one-sided type I error) and stop (for futility or safety collectively) at the interim analysis with probability about 0.75. When the true CRR is at least 30% or the true ORR is at least 60%, this design will successfully conclude with probability at least 0.62 (power) and stop at the interim analysis with probability at most 0.34. The schematic in Figure 1, immediately below, gives the full operating characteristics over all considered combinations of CRR and ORR when the true Grade 4+ AE rate is 32%. The blue-purple region denotes the true generating scenarios satisfying the ‘either-or’ hypothesis, wherein at least one of the efficacy thresholds is met or exceeded. The green region denotes satisfying neither the null nor the alternative hypothesis, wherein both efficacy rates exceed their null values but neither meets the alternative. The red region denotes the ‘both-and’ null hypothesis.

[figure not shown]

Figure 1: Probability of declaring success and, in parentheses, probability of stopping at the interim analysis for futility or toxicity, when the true Grade 4+ AE rate is 32%.

To demonstrate the effect of our toxicity stopping rule, Figure 2 below gives the operating characteristics of our design when the true Grade 4+ AE rate is 50%. The entire region is shaded red, because the treatment regimen is unacceptably toxic. The probability of declaring success, even when one of the efficacy thresholds is satisfied in truth, is always less than 0.16, and the trial stops at the interim analysis with probability at least 0.83.

[figure not shown]

Figure 2: Probability of declaring success and, in parentheses, probability of stopping at the interim analysis for futility or toxicity, when the true Grade 4+ AE rate is 50%.

Peripheral T-cell lymphoma response and progression will be assessed using the LYRIC criteria as outlined in section 9.

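### The prespecified toxicity thresholds stop at the interim: among patients 18 to 33 neither a drug-related death nor a high Grade 4+ rate meets a numeric enrollment stop or bars a declaration of success

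*Combined protocol and SAP*

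**What the plan says.** The synopsis (Statistical Considerations) introduces the safety rules with "Multiple Grade 4+ adverse event (AE) stopping rules will be applied during enrollment of the first 17 patients". Section 12.3 introduces them with "We will also formally incorporate three Grade 4+ adverse event (AE) thresholds that will activate at the interim analysis".

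The three rules in Section 12.3 are:
- Rule 1: "if the number of patients with any Grade 4 AE is greater than or equal to 7 (7/17=41%) by the interim analysis, enrollment will stop".
- Rule 2, for Grade 4 events that require discontinuation under Section 6.3: the count "is greater than or equal to 3 (3/17=12%) by the interim analysis, enrollment will stop".
- Rule 3: "enrollment will stop at the interim analysis for any Grade 5 AE attributable to drug". The synopsis words this one differently: "Third, enrollment will stop if any Grade 5 AE is observed within the first 17 subjects".

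The futility rule at the same look is: "if fewer than 3 patients demonstrate CR (<18%) and fewer than 7 patients demonstrate OR (<41%), the trial will be stopped for futility". If the trial continues, 16 more patients are enrolled, and success requires at least 7 CRs or at least 17 ORs among 33. That criterion has no toxicity term. Section 12.6 reports final safety as tables by grade and attribution.

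On a true Grade 4+ rate of 50%, Section 12.3 says: "The entire region is shaded red, because the treatment regimen is unacceptably toxic".

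Other oversight covers every patient: individual discontinuation rules (Section 6.3), SAE reporting within one business day (11.2.2.1 and 11.2.2.2), FDA 7- and 15-day reports (11.2.2.4), and DSMC review until the last subject finishes study drug (13.2).

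**The concern.** The second stage holds 16 of 33 patients, 48% of the sample, and no numeric safety boundary covers it. One drug-attributable death in patient 17, counted by the interim, stops enrollment. The same event in patient 18 meets no such rule. The rules as written allow up to 6 + 16 = 22 of 33 patients (67%) to have a Grade 4 event in a trial that is still declared a success, although the plan rejects a 50% rate.

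Two things are at stake. Whether enrollment pauses after a serious late signal is left to discretion, when the sponsor wanted fixed thresholds for the first half. And the success label can be issued without reference to toxicity that the plan itself would regard as unacceptable.

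**Working it through.** **Inputs (synopsis and Section 12.3).** Stages of 17 and 16. Futility stop if CR < 3 and OR < 7. Success if CR ≥ 7 or OR ≥ 17 of 33. Rule 1 at ≥ 7 of 17. Grade 4+ rates of 32% and 50%. Assumption: adverse events are independent of response.

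**Step 1: reproduce the plan's figures.** I enumerated the trinomial (CR, PR, no response) exactly over both stages and applied rule 1 once, at patient 17:
- P(Bin(17, 0.32) ≥ 7) = 0.284 and P(Bin(17, 0.50) ≥ 7) = 0.834.
- P(success) = P(efficacy success) × P(rule 1 not met).
- P(interim stop) = 1 − (1 − P(futility)) × P(rule 1 not met).

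| True CRR / ORR | Grade 4+ rate | Success | Interim stop | Plan states |
|---|---|---|---|---|
| 10% / 30% | 32% | 0.042 × 0.716 = 0.030 | 1 − 0.351 × 0.716 = 0.749 | < 0.05; about 0.75 |
| 30% / 30% (least favorable case found) | 32% | 0.867 × 0.716 = 0.621 | 1 − 0.923 × 0.716 = 0.339 | ≥ 0.62; ≤ 0.34 |
| 30% / 60% | 50% | 0.955 × 0.166 = 0.159 | 0.836 | < 0.16; ≥ 0.83 |

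The agreement shows that the stated figures contain no toxicity check after patient 17. They match rule 1 alone, so rules 2 and 3 appear not to be in the simulation.

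**Step 2: late toxicity.** Take CRR 30% and ORR 60%, with a Grade 4+ rate of 32% in the first 17 and 50% in the last 16 (illustrative). Success is 0.955 × 0.716 = 0.684, exactly as with 32% throughout, because no term depends on the second-stage rate. Yet P(Bin(16, 0.50) ≥ 8) = 0.598: in about six of ten such second stages at least half the patients would have a Grade 4+ event.

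**Step 3: carry rule 1 forward at the plan's own proportion.** 7/17 = 41%, and 33 × 7/17 = 13.6, so the count is 14 (14/33 = 42%). Given that rule 1 was not met at the interim (≤ 6 of 17):

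P(total ≥ 14) = 1 − P(≤ 6 of 17 and total ≤ 13) / P(≤ 6 of 17)
- 32% throughout: 1 − 0.6863/0.7162 = 0.042.
- 50% throughout: 1 − 0.0860/0.1662 = 0.482.
- 32% then 50%: 1 − 0.4703/0.7162 = 0.343.

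**Step 4: carry rule 3 forward.** The documents available give no usable risk for this population, so I assume 1% to 5% per patient. P(at least one in the last 16) = 1 − (1 − g)^16, which is 0.149 at 1%, 0.386 at 3% and 0.560 at 5%. Requiring also that none occurred in the first 17, (1 − g)^17 × [1 − (1 − g)^16], gives 0.125, 0.230 and 0.234.

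**Step 5: carry rule 2 forward.** A count of 3 is 17.6% of 17 but 9.1% of 33. Given ≤ 2 of 17 at the interim, an unscaled count of 3 over 33 is reached with probability 0.02, 0.19, 0.41 or 0.55 at assumed rates of 2%, 5%, 8% or 10%. Scaling gives 33 × 3/17 = 5.8, so 6 of 33. The same calculation with 6 gives at most 0.033 over those rates.

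**The case against.** The strongest reply is that oversight does not end at patient 17. A reader might infer that a late death or a run of Grade 4 events triggers nothing. The documents do not support that: such a death goes through SAE reporting within a business day and FDA reporting, individual discontinuation rules apply, and the DSMC can raise an immediate concern at any time. This stands, and it limits the point to the missing numeric enrollment stop. None of these routes carries a threshold, however, and the same oversight was supplemented by fixed rules for the first 17.

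Second, the plan discloses its figures at a 50% rate (success below 0.16, interim stop at least 0.83) and accepts them, and success is an efficacy conclusion with safety tabulated separately. Also fair: this is a design choice, not an error. But that disclosure assumes 50% from the first patient, and all its protection comes from the interim look. It says nothing about toxicity that emerges later.

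Third, a reader might credit continued monitoring with cutting success at a 50% rate from 0.159 to 0.082 (0.955 × 0.0860). That reduction needs a binding toxicity term in the success rule, which would also lower minimum power from 0.621 to about 0.595. A hold for review does not deliver it. Nor is 0.04 the whole chance of a pause: it covers rule 1 only.

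Finally, the 14 of 33 trigger is reached late if at all, so its value lies as much in reporting as in sparing patients exposure.

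**Conclusion.** The concern holds in this limited form. No prespecified enrollment stop covers patients 18 to 33, and toxicity there cannot alter the success declaration. The stated operating characteristics rest on one look at 7 of 17, so success is 0.684 whether the second-stage Grade 4+ rate is 32% or 50%. At 50% throughout, about one trial in six (0.166) passes rule 1, and 0.48 of those would go on to reach 14 of 33.

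The results assume independence of toxicity and response; the late-toxicity scenario and the death risks are illustrative. The gap is worth closing because the remedy is cheap. It is not evidence that late safety signals would go unreported, or that the plan's stated power or type I error is wrong.

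**What to change.** In Section 12.3 and the synopsis:
1. Extend monitoring through patient 33 as a non-binding hold on enrollment pending review by the existing DSMC. Trigger it by any drug-attributable Grade 5 event, or by a cumulative 14 of 33 patients with a Grade 4 event.
2. If rule 2 is carried forward, scale its count to 33 patients (6 at the same proportion) instead of keeping 3.
3. Report the CR/OR conclusion together with the cumulative toxicity result and whether 14 of 33 was reached.
4. Reconcile the two statements of the rules while editing: any Grade 5 event or only drug-attributable ones; during enrollment or at the interim; and the printed 12% for 3/17, which is 17.6%.

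The cost is wording plus possible enrollment pauses. After the interim is passed, the rule 1 trigger has probability 0.04 at a 32% rate and 0.48 at 50%. The Grade 5 trigger has probability 0.15 to 0.56 over the last 16 for an assumed death risk of 1% to 5%. Because the hold is non-binding, stated power and type I error are unchanged if enrollment resumes.

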1. BACKGROUND AND RATIONALE

1.1 Background: Peripheral T Cell Lymphoma (PTCL)

Approximately 10-15% of non-Hodgkin lymphomas (NHL) are derived from mature (i.e. post-thymic) T lymphocytes [1]. The heterogeneity of these lymphomas and poor understanding of their pathogenesis continue to impede their classification and the development of novel therapeutic strategies. This is highlighted by the sobering observation that the most common subtype of peripheral T-cell lymphoma (PTCL) lacks any distinguishing characteristics and is designated by the World Health Organization as “PTCL, not otherwise specified (PTCL, NOS)” [1, 2]. While the development of combination immunochemotherapy (e.g. “R-CHOP”) has led to significant survival benefits in B-cell NHL, the PTCLs are associated with inferior responses to therapy and overall survival [3]. In fact, the vast majority of PTCL patients will ultimately succumb to their disease, most within a few years of diagnosis [1, 2, 4]. Novel therapeutic strategies are needed if improved outcomes are to be achieved. The observation that PTCL incidence rates are increasing faster than almost any other subgroup of NHL further heightens this sense of urgency [5, 6].

Anthracycline-based therapies (e.g. CHOP) remain the mainstay of therapy for PTCL, even though the survival benefit associated with this approach remains suboptimal[2, 7]. More intensive induction regimens and consolidation with high-dose chemotherapy followed by autologous stem-cell transplantation are frequently employed strategies, but primary refractory disease and early relapses are common. Three novel agents, belinostat, pralatrexate and romidepsin, were granted FDA approval for relapsed/refractory PTCL and are associated with overall response rates of approximately 26% [8], 29%[9] and 25-38%[10, 11], respectively. A complete response rate of ~11% is observed in patients treated with belinostat or pralatrexate as single agents. Durable complete remissions are rarely achieved with these agents. Consequently, the outlook for PTCL patients with relapsed/refractory disease remains grim, and novel therapeutic strategies are needed[12, 13].

While preliminary results with checkpoint blockade (CPB) are encouraging, it is likely that novel combinatorial strategies will be required to improve outcomes in these patients following CPB [14].

Brentuximab vedotin also received FDA approved for the treatment of relapsed/refractory anaplastic large cell lymphoma (ALCL), a subtype of PTCL, based on phase II, open-label study of 58 patients. The overall response rate in this study was 86% with a complete response rate of 57% with a median duration of 13.2 months [15]. Grade 3/4 adverse events occurred in >10% of patients and included neutropenia, thrombocytopenia, and peripheral sensory neuropathy[15]. Another phase II, open-label, multicenter study evaluated the response rate of Brentuximab vedotin in relapsed CD30+ non-Hodgkin lymphomas which included PTCL and angioimmunoblastic T-cell lymphoma (AITL). The overall response rate in these cases was 41% with a complete response rate of 24% [16]. The duration of response is quite variable and short with the reported median duration of response of 7.6 months; however, the median duration of a complete response had not been reached at the time of the initial analysis[16]. Grade 3/4 events were similar to that of the ALCL study with neutropenia, peripheral sensory neuropathy and hyperkalemia being the most common events [16]. Brentuximab is a promising treatment agent but the most significant limitation is the need for continued treatment which is limited by cytopenias and peripheral neuropathy. Furthermore, the use of brentuximab within PTCL is limited to ALCL. Despite the use of these novel agents, the outlook for PTCL patients with relapsed/refractory disease remains grim, and novel therapeutic strategies are needed.

1.2 Background: Checkpoint blockade (CPB) in PTCL

While durable remissions with conventional chemotherapy are rarely achieved in relapsed/refractory T-cell NHL [12, 13, 17], durable remissions are achieved with immunomodulatory therapies, including extracorporeal photopheresis (ECP) and interferon- α [18]. While largely anecdotal, these observations suggest that host immunity, when properly harnessed, can lead to durable responses in selected patients. These observations, coupled with high-level PD-L1 expression in a substantial minority of patients, further provide a strong rationale for CPB in cutaneous T cell lymphoma (CTCL) and PTCL. While few of these patients have been included in early phase clinical trials and further experience with CPB in CTCL/PTCL is needed, few durable responses have been observed to date. Twenty-three CTCL/PTCL patients were enrolled in a phase Ib study with nivolumab in relapsed/refractory hematologic malignancies[19]. Among heavily pretreated (61% had received ≥ 4 prior therapies) CTCL/PTCL patients enrolled in this study, no complete remissions and 4 partial remissions were observed, for an overall response rate of 17% [19]. While the median progression-free survival was 10 weeks for all patients, two responding CTCL patients achieved responses that were ongoing at 24+ and 50+ weeks. A single PTCL patient achieved a response that was ongoing at 18+ months. Preliminary data from an ongoing phase II study with pembrolizumab in relapsed/refractory mycosis fungoides (MF) and Sezary syndrome (SS) has been reported[20]. Among 24 patients enrolled, no complete remissions and eight partial remissions were observed, for an overall response rate (ORR) of 33%. Among these responses, four were in MF (44% ORR in MF) and four in Sezary syndrome (27% ORR in SS). Responses were observed in advanced-stage MF, including patients with tumor-stage disease (2/2, ORR 100%) and large-cell transformation (1/3, ORR 33%). While these preliminary results are encouraging, improved understanding of the genomic and immunologic landscapes may be needed to further optimize CPB in the T-cell lymphoproliferative disorders.

